10.3. ANALYSIS OF SAFETY

Subjects in study will be evaluated for safety at Week 1 and 2. Subjects with tolerable toxicity will be allowed to continue study therapy for an additional 2 weekly treatments and possibly more at the discretion of the investigator.

Vital signs (systolic and diastolic blood pressure, and pulse), weight determinations and physical examination results will be summarized by treatment group using appropriate descriptive statistics. Continuous variables will be summarized using the number of observations, mean, standard deviation, minimum, median and maximum values. Categorical values will be summarized using number of observations and percentages.

Withdrawals from the study will be summarized by dose group.

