Title of the Study

A Phase 2a, Multi-center, Placebo-controlled, Randomized, Partially Blinded, Study of Infused METREXASSISTTM (Parenteral TK-112690) or MetrexassistTM Placebo Administered Along with Methotrexate Weekly for Four Consecutive Weeks to Patients with recurrent or residual SCCHN.

Principal Investigators Approximately 3

Study Centers Approximately 3

Clinical Phase

Phase 2a

Number of Subjects

The total number of individuals enrolled will be 22, 11 dosed TK-112690 and methotrexate and 11 patients dosed methotrexate and placebo. All patients will be dosed a nutritional supplement to assure adequate basal levels of uridine and uridine-related biochemicals.

Study Drug:TK-112690, an anhydrouridine inhibitor of uridine phosphorylase

Projected Subject Enrollment Duration

10 months

Objectives

Primary

Determine pilot efficacy of an iv infusion of TK-112690 to placebo as a mucositis preventive in subjects with locally advanced, residual, or recurrent or metastatic SCCHN scheduled to receive MTX as chemotherapy.

Secondary

Confirmation of the safety/tolerability of a continuous administered weekly for 4 weeks and lowering of plasma concentrations of surrogate markers of mucositis, e.g., CD40/CD40L, post TK-112690 in patients

suffering from local, advanced, residual or recurrent, metastatic SCCHN receiving sequential continuous iv infusions of TK-112690 and MTX or TK-112690 placebo and MTX.

Study Design

A Phase 2a, Multi-center, Placebo-controlled, Randomized, Partially Blinded, Study in Patients with recurrent or residual SCCHN.

Patients will receive MTX at a dose of 45 mg/m² administered weekly for **4 consecutive weeks** as an iv infusion along with a nutritional supplement containing uridine monophosphate (Fortasyn ConnectTM / SouvenaidTM, Nutricia NV) administered two hours before the MTX. One hour before the MTX treatment the patients will be administered the first infusion of the day of either TK-112690 or placebo depending on randomization infusion. Five hours after the MTX treatment the patients will be administered the second treatment of either TK-112690 or placebo depending on randomization. The TK-112690 dose will be 45 mg/kg.

- A total of 22 patients will be enrolled into one of 2 different dose groups: TK-112690 treated or placebo treated.
- Screening must be within 15 days of subject enrollment.
- Patients will remain for observation at the clinical site for a minimum of 25 hours post initial TK-112690 or placebo dose.

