- Study follow-up will occur on Week 6, two weeks after the last dosing of MTX.
- Blinding: The study will be partially blinded. The patient and investigator will be blinded as to whether TK-112690 or placebo is administered. The CRO,sponsor, and site pharmacist will know whether the patient was administered active drug or placebo.

Main Study Endpoints/Outcomes

• Mucositis Outcomes

Mucositis status in the patients will be evaluated using 4 different published and validated mucosit scales: OMAS/Sonis, PROMS, WHO, and CTCAE/mucositis.

• Surrogate Marker Outcomes

Plasma samples will be obtained to determine surrogate markers of mucositis, eg, CD40/CD40. TNF- α , etc.

• Safety Outcomes

Adverse events will be assessed throughout the study. Incidents of toxicity will be determined to at least possibly related to the study drug and graded according to CTCAE Version 4.0.

Study Procedures and Study Assessments

- A review of a patient's medical history including a detailed history of the patient's cancer and concomitant medications will be performed at screening.
- Screening for drugs of abuse will be performed at the time of patient screening and Day 0 (the day before start of study).
- Vital sign measurements will be performed at patient screening, on Day 0, and at 24 and 48

hours post each initial infusion of TK-112690/placebo as well as on Day 1 of Week 6.

- Physical examinations will be performed at screening, on Day 0, and 24 and 48 hours post each initial infusion of TK-112690/ placebo as well as on Day 1 of Week 6.
- ECOG performance status will be determined at patient screening, on Day 0, and at Day 1 of Weeks 6.
- For pre-menopausal females, a urine pregnancy test will be performed at screening, on Day 0, and at Day 1 of Week 6.
- 12-Lead ECG at screening and 24 hours post each initial infusion of TK-112690/ Placebo.
- CBC, Liver function test, Kidney function test determination at the clinical site prior to methotrexate treatment to ensure patient fit to dose.
- Serum chemistry, hematology, coagulation and urinalysis at screening, Day 0, and at 24 and 48 hours post each initial infusion of TK-112690/ placebo as well as on Day 1 of Week 6.
- Adverse events will be evaluated 5, 24 and 48 hours post each initial infusion of TK-112690/ Placebo as well as on Day 1 of Week 6.

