2.0. STUDY OBJECTIVES

2.1. PRIMARY OBJECTIVE

The primary objective of this study is to establish pilot efficacy compared to placebo for TK-112690 as an anti-mucositis agent when administered weekly for 4 weeks by iv infusion to subjects with locally advanced, residual or recurrent or metastatic SCCHN scheduled to receive MTX as chemotherapy.

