3.2. OVERVIEW OF STUDY DESIGN AND DOSING REGIMEN

This is a multi-center, randomized, partially blinded, placebo controlled, Phase 2a, pilot efficacy/safety study of $METREXASSIST^{TM}$ (parenteral TK-112690) administered weekly for 4 weeks in combination with MTX in subjects with SCCHN.

Figure 20 below provide, respectively, an overview of the study design.

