7.1. SCHEDULE OF EVENTS

Schedule of events are provided in **Table 12 below**. **Table 12.** Schedule of events (weekly cycle for 4 weeks and follow up at 6 week)

Englishting	Samooning	D. 0	Weeks 1, 2, 3, and 4					Week 6
Evaluation	Screening	Day 0	0h	5h	6h	24h	48h	Follow-up

Informed Consent ¹	Х							
I/E Criteria	Х							
Medical history ²	Х							
Test for drugs of abuse	Х	Х						
Physical examination ^{3,4}	Х	Х				X ⁵	X ⁵	Х
Vital signs and weight	Х	Х				X^6	X ⁶	X^6
ECOG	Х	Х						Х
Pregnancy test (females)	Х	Х						Х
12-Lead ECG	Х					Х		
Laboratory tests ⁷	Х	Х				Х	Х	Х
Randomization		Х						
CBC, Kidney function test, Liver Function test		X^8						
Nutritional supplement			X ⁹					
TK-112690/placebo treatments ¹⁰			X^{10}		X ¹³			
MTX treatment			X ¹¹					
Surrogate marker sample			X ¹²	Х		Х	Х	Х
Mucositis evaluation ¹⁴		Х				Х	Х	Х
Disease Status	Х							Х
AEs assessment				Х		Х	Х	Х
1 To be obtained before any	study-related	activities at	e perform	-d				

¹ To be obtained before any study-related activities are performed.

² Include a review of previous/ongoing medications for 180 days prior to enrollment.

³ Complete examination, including assessments of the skin, head, eyes, ears, nose, throat, neck, thyroid, lungs,

heart, abdomen, lymph nodes, extremities, and body weight.

⁴ Height will be measured at screening only.

⁵ Partial examinations to update findings from the examination performed at screening.

⁶ Include blood pressure, pulse, respiratory rate and temperature.

⁷ Includes serum chemistry, hematology (including coagulation), urinalysis; Hepatitis B/C & HIV only at screening

⁸ CBC, Kidney function test, Liver Function test at clinical site can be performed anytime within 24 hours of a methotrexate treatment (NEEDED FOR ALL MTX TREATMENTS, EG, TREATMENTS ON WEEKS 1, 2, 3, AND 4, TO VERIFY OK TO DOSE MTX)

⁹One hour before TK infusion/placebo

¹⁰ Beginning of TK-112690/placebo infusions is 0 hours. Dose is 45 mg/kg.

^{11 45} mg/m² one hour after TK-112690/placebo infusion.

¹² Pre-dose control samples for surrogate marker measurements.

¹³6 hours after TK-112690/placebo treatment, ie, 5 hours post MTX treatment

¹⁴See Section 20.6 for mucositis assessment scales.

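### Section 10.3 permits weekly treatments beyond four, contradicting the four-week regimen; if used before Week 6, the only post-treatment visit could become an on-treatment one for those patients

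*Combined protocol and SAP*

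**What the plan says.** Section 10.3 opens with a safety check: "Subjects in study will be evaluated for safety at Week 1 and 2". Patients whose toxicity is tolerable may then "continue study therapy for an additional 2 weekly treatments and possibly more at the discretion of the investigator". Nothing else in the document limits or explains the last part of that sentence.

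Other places fix the duration at four weekly treatments:

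- Title in the Study Synopsis: "Weekly for Four Consecutive Weeks".
- Section 2.1 (Primary Objective): "administered weekly for 4 weeks by iv infusion".
- Section 3.2 (Overview of Study Design): "administered weekly for 4 weeks in combination with MTX in subjects with SCCHN".
- Table 12 in section 7.1: "Schedule of events (weekly cycle for 4 weeks and follow up at 6 week", with treatment columns for Weeks 1 to 4 only.
- Section 7.1.3 sets out the dosing-day procedures for Weeks 1 to 4 and no later week.

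The synopsis (Study Design) ties the follow-up visit to the last dose: "Study follow-up will occur on Week 6, two weeks after the last dosing of MTX". The Follow-up paragraph of the synopsis says the same of the study drug and names Day 1 of Week 6. Sections 5.2 and 7.1.4 apply that visit to all patients.

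**The concern.** Two operative statements disagree on how many weekly treatments a patient may receive, and the analysis plan does not say what happens to data from a patient who receives more than four.

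Week 6 is the only scheduled assessment after treatment ends. It covers mucositis, surrogate markers, laboratory tests, ECOG status, adverse events and tumor status by CT. If an investigator extends treatment before that visit, the patient contributes an on-treatment value to a summary meant to be post-treatment. Extension is conditional on tolerable toxicity, and the trial tests whether the drug reduces a toxicity of methotrexate (MTX). The proportion extended could therefore differ by arm as a consequence of treatment. With 11 patients per arm and descriptive summaries, a few such patients could shift an arm's Week 6 result.

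No existing rule contains this. The efficacy population in section 10.2.1 sets a minimum number of doses and no maximum. Section 10.3.2 tabulates laboratory abnormalities at the last visit without defining it for an extended patient. No assessments are scheduled for a treatment in Week 5 or later.

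**Working it through.** **Inputs.** Weekly treatment on Day 1 of each of Weeks 1–4, with follow-up on Day 1 of Week 6 (synopsis, Table 12). Dosing tolerance of ± one day (section 5.3). Treatment holds of up to 2 weeks before permanent discontinuation (section 3.1.2). Sample and blood-volume totals (section 6.7.3 and Table 11).

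**Number of treatments implied by section 10.3.** 2 (Weeks 1 and 2) + 2 further = 4. Anything beyond is a fifth or later treatment.

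**Reproducing the plan's own interval.** Day 1 of Week w is study day 7(w − 1) + 1.

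- Fourth treatment: 7 × 3 + 1 = Day 22.
- Follow-up: 7 × 5 + 1 = Day 36.
- Gap: 36 − 22 = 14 days, the stated two weeks (13 to 15 if the fourth treatment moves by one day).

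**Do the plan's other totals also assume four cycles?**

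- Marker samples: 4 × 4 + 1 = 17, as stated.
- Blood volume: 7 × 4 + 14 × (3 + 2 × 4) + 5 × 17 = 28 + 154 + 85 = 267 mL, as stated.
- With five full cycles these would be 21 samples and 35 + 182 + 105 = 322 mL. With six they would be 25 samples and 42 + 210 + 125 = 377 mL.

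**If treatment continues weekly beyond Week 4:**

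| Weekly treatments | Last treatment | Days to Week 6 visit | Treatments relative to four |
|---|---|---|---|
| 4 | Day 22 | 14 | 4/4 = 1.00 |
| 5 | Day 29 | 7 | 5/4 = 1.25 |
| 6 | Day 36 | 0 | 6/4 = 1.50 |
| 7 | Day 43 | −7 (visit comes first) | 7/4 = 1.75 |

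On a sixth treatment day, if scoring precedes dosing, the Week 6 value falls 7 days after the fifth treatment and reflects five treatments, not six.

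**Holds.** If a held treatment is postponed rather than omitted (the protocol does not say which), a one-week hold moves the fourth treatment to Day 29 and a two-week hold to Day 36. The gaps are 7 and 0 days, with no extra treatment given.

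**Reach.** Mucositis is scored at 24 and 48 hours in each of Weeks 1–4 (4 × 2 = 8) and once at Week 6, so there are 9 post-baseline assessments. Eight precede any fifth treatment.

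**The case against.** The strongest reply is that the consequence is conditional and narrow. Section 10.3 gives no timing for further treatment. If it came after Day 1 of Week 6, the Week 6 data would be intact. Patient and investigator are blinded, so the discretion is not exercised with knowledge of the arm. Section 3.1 names mucositis scores without making Week 6 the primary timepoint, and CT response is not among its key endpoints. All of this stands and limits the size of the point. It does not remove the contradiction: every other statement of duration says four, and blinding does not prevent a tolerability-driven difference between arms.

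Three stronger readings are tempting, and the documents support none of them.

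- A reader might infer that some patients will be on treatment at Week 6. The text only permits it, and nothing indicates how often the permission would be used.
- A reader might count the 28-day adverse-event window in section 9.1.4 as a further defect because it would move with extra doses. It runs from the last intake and already moves after early discontinuation; extending it to cover extra doses is appropriate handling.
- A reader might attribute the whole range of 25–50% more treatments and a 0–7 day gap to one patient. These are separate cases, as the table shows.

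It is also fair to object that section 10.3 is not the only cause, since holds can shorten the interval in the same way. That argues for an analysis rule covering both.

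**Conclusion.** The contradiction is established from current text. Section 10.3 allows an unlimited number of weekly treatments, whereas the regimen, the schedule, the stated follow-up interval and the sample totals all assume four. If the discretion is used before Week 6, the interval to the visit falls from 14 days to 7 (five treatments) or 0 (six), and treatment exposure rises by 25% or 50%.

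This assumes that extra treatments follow weekly without a break and include MTX as in Weeks 1–4; section 10.3 states neither. An imbalance between arms is possible, but the documents give no figure for it. The Week 1–4 mucositis comparison is untouched by extra treatments. No power figure is affected, because section 10.1.1 says the sample size was not calculated. The point should be corrected before the analysis is fixed, but it does not threaten the trial as a whole.

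**What to change.** 1. Reconcile section 10.3 with the title, section 2.1, section 3.2, Table 12 and section 7.1.3 on the number of weekly treatments. Which statement holds is for the sponsor to decide.
2. Whichever holds, state in section 10 that the main arm comparisons of mucositis, surrogate markers and safety use data through the fourth weekly cycle.
3. Report Week 6 data for all patients with days since last dose. Flag patients without the two-week interval, whether from extra treatments or from holds, and summarise them separately. Do not discard their data: exclusion would create missingness related to tolerability.
4. List any additional doses by arm.

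The cost is wording in section 10, plus one derived variable (days since last dose) and one listing. No visit, sample or patient is added.

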10.3.1. Incidence of Adverse Events

Adverse events will be classified and graded according to the NCI Common Terminology Criteria for Adverse Events (CTCAE), version 3.0.

The primary safety analysis using descriptive statistics will include summaries of incidence rates, severity, and type of adverse events; summary of changes in subjects' clinical laboratory results; and summaries of the number of toxicity grades for laboratory and non-laboratory data.

Adverse events will be coded using the MedDRA adverse event dictionary. Frequency of treatment emergent adverse events will be calculated for each body system, by preferred term, by treatment group, for number of subjects and proportion reporting the event. The severity of the adverse events and the relationship to study medication will be summarized for each body system and preferred term by treatment group. Withdrawals due to adverse events will be summarized for each body system and preferred term by treatment group.

10.3.2. Laboratory Data

The number and percentage of subjects with laboratory abnormalities at the screening visit and the final visit (or early withdrawal) will be tabulated.

Descriptive statistics (number of observations, mean, standard deviation, minimum, median and maximum values) will be calculated for clinical laboratory tests (hematology, serum chemistry, and urinalysis) at applicable visits.

10.4. SUBJECT ACCOUNTABILITY AND MISSING DATA

Data from subjects lost to follow-up will be tabulated and any difference between those subjects and subjects not lost to follow-up will be noted.

10.5. INTERIM ANALYSIS

No interim analyses will be performed.

11.0. DIRECT ACCESS TO SOURCE DATA / DOCUMENTS AND INVESTIGATOR RESPONSIBILITY

It is understood that the term "PI" as used in this protocol and on case report forms refers to the Principal PI or a member of the staff that the Principal PI designates to perform a certain duty. However, on specific CRFs the investigator him/herself is required to sign where indicated. The Principal PI is ultimately responsible for the conduct of all aspects of the study.

The PI will ensure that this study is conducted in full conformance with the principles of the "Declaration of Helsinki" (as amended in Tokyo, Venice, Hong Kong, Somerset West, and Edinburgh) and with the laws and regulations of the country in which the research is conducted, whichever affords the greater protection to the individual.

It is the responsibility of the PI to obtain written informed consent from each individual participating in this study, after adequate explanation of the aims, methods, objectives and potential hazards of the study. The PI must also explain to the subjects that they are completely free to refuse to enter the study or to withdraw from it at any time. The document must contain all the elements described in 21 CFR, Part 50 and ICH Guidelines.

The PI shall make accurate and adequate reports to Tosk and/or its representative and to the EC/IRB on the progress of the study at appropriate intervals. Additionally, the PI shall make accurate and adequate final status reports, through completed CRFs, to the monitors and to the IRB within three weeks after the completion, termination, or discontinuation of the study. The final report must include all case report forms that were not previously provided to the monitors.

Qualified representatives of the sponsor or sponsor designees ("study monitors") will monitor the study according to a predetermined monitoring plan. Monitoring visits provide the sponsor with the opportunity to:

• Evaluate the progress of the study.

- Verify the accuracy and completeness of CRFs.
- Assure that all protocol requirements, applicable laws and/or regulations, and PI's obligations are being fulfilled.
- Resolve any inconsistencies in the study records.

The PI must allow the study monitors to periodically review, at mutually convenient times during the study and after the study has been completed, all CRFs and office, hospital, and laboratory records supporting the participation of each subject in the study. The CRFs and other documentation supporting the study must be kept up-to-date by the PI and the research staff at the investigative site. These study materials must be available for review by the study monitor, and/or other qualified representatives of the sponsor, at each monitoring visit.

The study monitor will regularly inspect the various records of the study (CRFs, subject medical and laboratory records, and other pertinent data) provided that subject confidentiality is maintained in accordance with local institution, state, country, and federal requirements. The study monitor will verify the data against other source documentation in order to verify its accuracy and completeness. The study monitor will identify data discrepancies and collaborate with the PI and research staff to resolve the discrepancies in the CRF in a timely manner. The study monitor will generate queries as required using the CRF system. Protocol deviations will also be identified and recorded on a "Protocol Deviation Log". The study monitor will follow an "Issue Escalation" plan in order to ensure that each issue identified during a monitoring visit is appropriately documented, reported, and resolved in a timely manner in accordance with the plan's requirements.

11.1. SUBJECT INFORMATION AND CONSENT

The PI will ensure that the subject is given full and adequate verbal and written information about the nature, purpose, possible risk and benefit of the study. Subjects, legal guardian or responsible relative must also be notified that they are free to discontinue their participation in the study at any time. The subject legal guardian or responsible relative should be given the opportunity to ask questions and, when possible, time for consideration. The PI is responsible for obtaining signed informed consent from all subjects before enrollment. In subjects unable to consent to treatment, consent must be obtained from a close family member or legal guardian in writing before enrollment.

A copy of the subject information including the signed Consent Form should be retained by the subject.

11.2. SUBJECT CONFIDENTIALITY

All data computer-processed at Tosk or by its designee will be identified by subject number only, thereby ensuring that the subject's identity remains unknown to the sponsor. The subjects should be informed in writing that the data will be stored and analyzed in a computer, maintaining confidentiality in accordance with national data legislation. The subjects should also be informed in writing that authorized representatives of the company and/or Regulatory Authorities, may require access to those parts of the hospital/practice records relevant to the study, including medical history, for verification of data. The Principal PI is responsible for keeping a subject identification list or form of all subjects enrolled, including enrollment code, subject number, full name and address.

11.3. SOURCE DATA

Source data is defined as all information in original records and certified copies of original records of clinical findings, observations or other activities in a clinical trial necessary for the reconstruction and evaluation of the trial. Source data are contained in source documents (original records or certified copies).

11.4. SOURCE DOCUMENTS

Source documents are defined as original documents, data and records (eg, hospital records, clinical and office charts, laboratory notes, memoranda, subject diaries or evaluation check lists, pharmacy dispensing records, recorded data from automated instruments, copies or manuscripts certified after verification as being accurate copies, microfiches, photographic negatives, microfilm or magnetic media, x-rays, subject files, records kept at pharmacy, at the laboratories and at medico technical departments involved in the clinical trial).

